#### 4.1.3 RATE OF REFRACTIVE PREDICTABILITY AT 3 MONTHS POSTOPERATIVE

The achieved MRSE is defined as "Postop MRSE – Targeted MRSE". The frequency, proportion and 95% confidence intervals of eyes with achieved MRSE within 0.50 D and 1.00 D of targeted MRSE will be summarized at 3 months postoperatively. The proportion of study group eyes with achieved MRSE within 0.50D and within 1.00D of targeted MRSE is expected to be greater compared to control group eyes. The right eyes and left eyes data from each group will also be presented.

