- Rate of refractive predictability (i.e., within 0.50 D of target refraction, and within 1.00 D of target refraction) at 3 months postoperative for the Study and Control groups.
- Rate of bothersome ocular symptoms (halos, night glare, starbursts, and night vision difficulties) at 3 months postoperative for the Study and the Control groups.
- Mean change in total meibomian gland score in the Study group compared to the Control group from Baseline to the 1-month postoperative visit.

Other Endpoints:

- 1-Month Postoperative Visit:
 - Mean change in Number of Meibomian Glands Yielding Liquid Secretion (MGYLS) from Baseline visit to 1 month postoperative in the Study group compared to the Control group.
 - Mean change in ocular surface stain grade from Baseline visit to 1 month postoperative in the Study group compared to the Control group.
 - Mean change in Tear Break-up Time (TBUT) from Baseline visit to 1 month postoperative in the Study group compared to the Control group.
 - Mean change in Eyelid Margin Evaluation from Baseline visit to 1 month postoperative in the Study group compared to the Control group.
- 3-Months Postoperative Visit:
 - Mean monocular BCDVA in the Study group at 3 months postoperative compared to the Control group.
 - Mean binocular UCDVA and BCDVA in the Study group at 3 months postoperative compared to the Control group.
 - Mean binocular UCIVA in the Study group at 3 months postoperative compared to the control.
 - Mean binocular UCNVA in the Study group at 3 months postoperative compared to the Control group.
 - Mean manifest refraction spherical equivalent (MRSE) at 3 months postoperative compared to target MRSE in the Study group compared to the Control group.
 - Contrast acuity in the Study group at 3 months postoperative compared to the Control group.
 - Mean change in total Standard Patient Evaluation of Eye Dryness (SPEED) score from Baseline visit to 3 months postoperative in the Study group compared to the Control group.
 - Mean change in total meibomian gland score in the Study group compared to the Control group from Baseline to 3 months postoperative.
- Control Group 4-Months Postoperative Visit:
 - Mean change in monocular UCDVA and BCDVA from 3 months to 4 months postoperative.
 - Mean change in binocular UCDVA and BCDVA from 3 months to 4 months postoperative
 - Mean change in binocular UCIVA from 3 months to 4 months postoperative
 - Mean change in binocular UCNVA from 3 months to 4 months postoperative

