Predicted postoperative corneal astigmatism, as measured by keratometry, should be less than 1.00 D. No irregular astigmatism should be present preoperatively. If the preoperative keratometric astigmatism is greater than 0.50 D, assess the impact of posterior corneal astigmatism (PCA) on predicted residual astigmatism by using a calculator that accounts for PCA (e.g., J&J TECNIS Toric Calculator, Barrett Toric Calculator, etc.).

IOL POWER AND TARGETED REFRACTION

Axial length and anterior chamber depth (ACD) must be measured to determine the appropriate lens power to implant using an A-Constant. Non-contact biometry is preferred; however, surgeons should use the biometry method with which they have the most experience and which was used in the determination of personalized A-Constants for the Symfony lens.

The lens power should be calculated to achieve emmetropia at distance. Intentional over- or under-correction (outside ± 0.50 D) should NOT be planned for either eye;

however, surgeons may adjust the targeted refraction as necessary to achieve emmetropia based on surgeon factors, study subject experience and/or subject first-eye outcomes.

ADDITIONAL PREOPERATIVE EXAMINATION PROCEDURES AT PREOPERATIVE VISIT #1:

- Informed consent documentation
- Subject demographic information
- Planned surgery dates for each eye
- Cataract type and density for each eye
- Potential visual acuity, targeted refraction, IOL power calculations for each eye
- Fundus exam results for each eye
- Ocular surface staining for each eye
- Eyelid margin evaluation for each eye
- TBUT for each eye
- Meibomian gland imaging through LipiScan / LipiView II for each eye
- Ocular / Visual symptoms assessment (non-directed; spontaneous)
- PRVSQ questionnaire
- Ocular and systemic medications
- SPEED questionnaire
- Adverse events

Note that if the subject had a recent dilated retinal exam performed at the study site within 60 days prior to the Preoperative Visit #1, the prior examination data may be used for the baseline dilated retinal exam with the date of the dilated exam documented.

Randomization and Enrollment

Randomization will take place after the subject has signed the informed consent document and has met all inclusion and exclusion criteria. As part of the informed consent process, the investigator or delegate will explain to the subject the requirements of a randomized study and the differences expected between the two groups.

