#### 4.2.2 ENDPOINTS EVALUATED AT 3-MONTH POSTOPERATIVELY

Mean LogMAR monocular BCDVA, mean LogMAR binocular UCDVA, UCIVA, UCNVA, BCDVA and contrast acuity will be reported for study group eyes/subjects and control group eyes/subjects at 3 months postoperatively. Better visual acuity outcomes (lower mean LogMAR scores) for study group eyes are expected compared to control group eyes.

Summary statistics (mean, standard deviation, median, minimum and maximum) will be reported for MRSE at 3 months postoperative visit for study group eyes and control group eyes. The difference between MRSE at 3 months postoperative visit and the target MRSE will be calculated. The difference is expected to be smaller (closer to zero) for study group eyes than that for control group eyes.

Mean change in total Standard Patient Evaluation of Eye Dryness (SPEED) score from Baseline visit to 3 months postoperative in the study group subjects will be compared to the control group subjects. The SPEED score is the sum of frequency and severity scores with a range from 0 to 28. A lower SPEED score represents less frequent and/or less severe dry eye symptoms. The mean SPEED score will be reported at Baseline and 3 months postoperative visit. Greater mean change in SPEED score from Baseline to 3 months for study group subjects is expected.

Mean change in total Meibomian gland score from Baseline visit in the study group eyes will be compared to the control group eyes. Greater mean change in total Meibomian gland score is expected for study group eyes than that for control group eyes.

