### 4.2.3 ENDPOINTS EVALUATED AT 4-MONTH POSTOPERATIVE FOR CONTROL GROUP SUBJECTS ONLY

Mean change in LogMAR monocular BCDVA and UCDVA and mean change in LogMAR binocular UCDVA, UCIVA, UCNVA, BCDVA and contrast acuity will be reported for control group eyes from 3 months to 4 months postoperative visit. Better visual acuity outcomes (lower mean LogMAR scores) at 4 months visit are expected.

Mean MRSE at 4 months postoperative will be compared to target MRSE. Frequency and percent of eyes with MRSE within 0.50 D and within 1.00 D of target MRSE at 4 months postoperative will be reported.

Version 1.0 5 SAP/DRYE-102-SELF

Mean change in total Meibomian gland score and mean change in total SPEED score from 3 months to 4 months postoperative will be reported. An increase in both mean total Meibomian gland score and mean total SPEED are expected.

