#### **APPENDIX I: TABLE LISTING**

Variable	All Subjects	Study/control group	Note
ENROLLMENT/PREOP/OP			
Accountability/Enrollment			
Subjects/eyes by investigational site (n)	x	X	Subjects and eyes
Accountability table over time – (Available for analysis, Missing data –Forms not yet completed, Active, Missed visit, Lost to follow-up, Discontinued) (n and %)	Х	х	Subjects and eyes
Out of Interval listing	Х	Х	Subjects and eyes
Demographics			
Demographic – Age in years (N, Mean, SD, Min, Max), race, sex, ethnicity (n and %) Age in groups (<30, 30-39, 40-49, 50-59, 60-69, ≥70) (n, %)	х	х	Subjects
Preoperative Characteristics			
Target refraction (MRSE) - (N, Mean, SD, Min, Max)		x	eyes
BSCVA in groups (≤20/30, 20/40, 20/50-20/80, 20/100, >20/100) – (n,%)		х	eyes
Total Meibomian gland score at 1 st preop visit (baseline)- (N, Mean, SD, Min, Max, 95% CI)		х	eyes
Number of MGYLS at 1 st preop visit (baseline) – (N, Mean, SD, Min, Max, 95% CI)		x	eyes
TBUT at 1 st preop visit (baseline) – (N, Mean, SD, Min, Max, 95% CI)		x	eyes
SPEED score at 1 st preop visit (baseline) – (N, Mean, SD, Min, Max, 95% CI)		x	eyes
Eyelid margin evaluation assessment (obvious/minimal changes/normal appearance; Obvious/Non-obvious MGD) at 1st preop visit (baseline) – (n, %)		х	eyes
KEY STUDY ENDPOINTS			
Mean monocular UCDVA at 3-month (N, Mean, SD, Min, Max, 95% CI of LogMAR)		х	Eyes, also by right eye and left eye

Precision (avg. of SD from 3 sets of measurements) of preop (2 nd visit) AL, ACD and Ks	x	Eyes, also by right eye and left eye
Rate of MRSE predictability at 3-month (achieved MRSE within 0.5D/1.0D of target MRSE) – (n, %)	х	Eyes, also by right eye and left eye
Rate of bothersome ocular symptoms at 3-month – (n, %)	х	subjects
Mean change in total Meibomian gland score from baseline to 1- month – (N, Mean, SD, Min, Max, 95% CI)	х	Eyes, also by right eye and left eye
ENDPOINTS EVALUTED AT 1-MONTH POSTOP		
Mean change in number of MGYLS from baseline – (N, Mean, SD, Min, Max, 95% CI)	х	eyes
Mean change in ocular surface stain grade from baseline— (N, Mean, SD, Min, Max, 95% CI)	х	eyes
Mean change in TBUT from baseline- (N, Mean, SD, Min, Max, 95% CI)	х	eyes
Eyelid margin evaluation assessment (obvious/minimal changes/normal appearance; Obvious/Non-obvious MGD) at 1-month – (n, %)	х	eyes
ENDPOINTS EVALUTED AT 3-MONTH POSTOP		

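### SAP 4.1.3, read literally, subtracts the refractive target twice; two 4-month rows in Appendix I use the wrong reference visit; and the expected SPEED change after crossover has the wrong sign

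*SAP*

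**What the plan says.** **Refractive predictability at 3 months (key endpoint).** SAP 4.1.3 opens with a definition: "The achieved MRSE is defined as 'Postop MRSE – Targeted MRSE". The same section then reports the "proportion and 95% confidence intervals of eyes with achieved MRSE within 0.50 D and 1.00 D of targeted MRSE". The matching row in SAP Appendix I repeats the term: "Rate of MRSE predictability at 3-month (achieved MRSE within 0.5D/1.0D of target MRSE".

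Elsewhere the target enters once:
- Protocol synopsis: "Rate of refractive predictability (i.e., within 0.50 D of target refraction, and within 1.00 D of target refraction".
- SAP 4.2.2: "The difference between MRSE at 3 months postoperative visit and the target MRSE will be calculated".
- SAP 4.2.3, for the control group at 4 months: "Frequency and percent of eyes with MRSE within 0.50 D and within 1.00 D of target MRSE".
- Protocol 6.1 and 20.2 use the same counting sentence as SAP 4.1.3 but do not define achieved MRSE as a difference.

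**Targets.** Protocol 10.3 aims at emmetropia and adds: "Intentional over- or under-correction (outside ± 0.50 D) should NOT be planned for either eye". Appendix I plans to summarise the target itself: "Target refraction (MRSE) - (N, Mean, SD, Min, Max".

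**Control group at 4 months.** SAP 4.2.3 and Protocol 6.2 and 20.3 specify the change from 3 to 4 months for SPEED and for total Meibomian gland score. In the 4-month block of Appendix I, the rows for these two measures give the change from baseline.

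**Direction of SPEED.** SAP 4.2.3 and Protocol 20.3 expect both the gland score and SPEED to increase after crossover treatment. SAP 4.2.2 says that a lower SPEED score means fewer or milder symptoms.

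**The concern.** In SAP 4.1.3 the defined term is already net of target, and the counting rule compares it with the target again. A programmer who follows the SAP to the letter would shift the acceptance window by one full target value. Some eyes that met the target would be counted as misses, and some misses as hits. The control group's 4-month rate uses plain MRSE, so a literal 3-month rate would be on a different definition from the rate that follows it.

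The two Appendix I rows matter because the crossover is meant to show what treatment after the 3-month visit does. A change from baseline to 4 months also contains surgery and three months of recovery. If the tables were built from the listing, two protocol endpoints would not be produced.

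The SPEED sentence has no test attached and alters no computed value. It does state an expected benefit as a worsening.

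**Working it through.** The plan gives no figure for this point, so there is none to reproduce. The check substitutes the definition into the rule, tries it on single eyes, and then sizes it under stated assumptions.

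**1. Substitution.** Let T be the target, P the postoperative MRSE, and X = P − T the prediction error. SAP 4.1.3 calls X the achieved MRSE.
- Intended rule: |X| ≤ L, with L = 0.50 or 1.00 D.
- Literal rule: |X − T| ≤ L, that is |P − 2T| ≤ L.

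The two agree when T = 0.

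**2. Single eyes, T = −0.25 D, L = 0.50 D.**
- P = +0.25 D: X = +0.50, a hit. Literally, 0.50 + 0.25 = 0.75, a miss.
- P = −1.00 D: X = −0.75, a miss. Literally, −0.75 + 0.25 = −0.50, a hit.

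**3. Effect on the rate.** Neither the SD of X nor the distribution of targets is in the documents. Assume X is Normal with mean 0 and SD s.
- Correct rate = Φ(L/s) − Φ(−L/s).
- Literal rate = Φ((T + L)/s) − Φ((T − L)/s).
- Wrongly counted = probability that exactly one of the two rules holds.

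For s = 0.45, L = 0.50, T = −0.25:
- Correct: Φ(1.111) − Φ(−1.111) = 0.8667 − 0.1333 = 0.733.
- Literal: Φ(0.556) − Φ(−1.667) = 0.7107 − 0.0478 = 0.663.
- Hits lost: 0.8667 − 0.7107 = 0.156. Misses gained: 0.1333 − 0.0478 = 0.0855. Wrongly counted: 24.1%.

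The same formulas with s = 0.45 give:

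| Target | Within 0.50 D, literal | Wrongly counted at 0.50 D | Within 1.00 D, literal |
|---|---|---|---|
| 0 (correct rate) | 73.3% | 0% | 97.4% |
| −0.10 D | 72.2% | 9.6% | 97.0% |
| −0.25 D | 66.3% | 24.1% | 94.9% |
| −0.50 D (every eye at the limit) | 48.7% | 48.7% | 86.6% |
| Even over ±0.125 D | 72.7% | 6.0% | not computed |
| Even over 0 to −0.25 D | 71.0% | 12.0% | not computed |
| Even over ±0.50 D | 64.5% | 24.2% | not computed |

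At T = −0.25 D the rate within 0.50 D falls from 84.7% to 74.6% if s = 0.35, and from 63.7% to 58.9% if s = 0.55.

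**4. Effect on the comparison of arms.** Assume s = 0.40 in the study arm and 0.50 in the control arm, with the same target in both. The correct difference within 0.50 D is 78.9% − 68.3% = 10.6 points. Literally it is 10.1 points at −0.10 D, 7.9 at −0.25 D and 1.7 at −0.50 D. The difference shrinks but keeps its sign. When targets and errors are alike in both arms, the rule creates no spurious difference.

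**5. The 4-month block of Appendix I.** Five rows report a change. Three (monocular acuity, binocular acuity, contrast) use 3 to 4 months. Two (SPEED, gland score) use baseline, in the wording of the corresponding 3-month rows. Since

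(4 months − baseline) = (3 months − baseline) + (4 months − 3 months),

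only the last term is the crossover change that SAP 4.2.3 asks for.

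**6. SPEED.** The scale runs from 0 to 28 and lower is better (SAP 4.2.2). Protocol 17 expects LipiFlow to improve dry eye symptoms. The expected change after crossover is therefore a decrease. For the gland score, where higher is better, the stated increase is right.

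**The case against.** The strongest reply is that nobody would program the literal rule. The synopsis states the endpoint in full with one subtraction, Protocol 6.1 and 20.2 use achieved MRSE in the ordinary sense of the postoperative value, and no text supports doubling the target. Protocol 10.3 and 10.4 aim at emmetropia, so most targets should lie close to zero, where the rules nearly coincide. At −0.05 D the literal rate is 73.1% against 73.3%. With targets even over ±0.125 D the difference between arms is 10.4 points against 10.6. The rate has no test or success criterion; only UCDVA has one. The two Appendix I rows look like a copying slip, and both measures are collected at 3 and 4 months, so the right change can always be computed.

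Most of this stands, and it limits the size. The larger figures above depend on assumed targets that an emmetropic plan would make uncommon. It does not make the text correct. SAP 4.1.3 is the only definition of the term, the table listing carries the term forward, and the SAP should fix the computation of a key endpoint without the reader having to infer it.

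**Conclusion.** The concern holds. As written, SAP 4.1.3 gives the wrong rule for a key endpoint, two Appendix I rows name the wrong reference visit, and the SPEED expectation runs against its own scale. All three are drafting errors, and the intended meaning is clear from the rest of the documents.

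The practical effect of the first depends on how far targets lie from zero: none at 0 D, about 1 point on the rate within 0.50 D at −0.10 D, and 5 to 10 points at −0.25 D for an error SD of 0.55 to 0.35 D. These sizes rest on a Normal error centred at zero and on targets that the documents do not give. The second affects two descriptive, non-key outputs in one arm. The third is an erratum only. Sample size, power, alpha and the UCDVA criterion are untouched. It should be fixed before the tables are programmed.

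**What to change.** - **SAP 4.1.3:** replace the definition and rule with: Refractive prediction error = postoperative MRSE − target MRSE. Report the number, percentage and 95% CI of eyes with an absolute prediction error of at most 0.50 D, and of at most 1.00 D, at 3 months. Because a targeted refraction is recorded at both preoperative visits (Protocol 10.3, 10.4 and Appendix B), also state which record supplies the target.
- **SAP Appendix I, key-endpoint row for MRSE predictability:** use the same term and limits.
- **SAP Appendix I, 4-month block:** in the SPEED and gland-score rows only, change the reference visit from baseline to 3 months.
- **SAP 4.2.3 and Protocol 20.3:** say that mean gland score is expected to rise and mean SPEED to fall. Define SPEED change as follow-up minus reference visit, so that negative values are improvement.

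The cost is one definition, three table rows and one sentence in each document. No new data are needed, and neither the sample size nor the UCDVA analysis changes.

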#### 4.1.4 RATE OF BOTHERSOME OCULAR SYMPTOMS AT 3 MONTHS POSTOPERATIVE

The frequency and proportion of subjects who experienced moderate or severe ocular symptoms (halos, night glare, starburst, and night vision difficulties) will be reported. The rate of bothersome ocular symptoms at 3 months postoperatively is expected to be lower for study group subjects than that for control group subjects.

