- Mean MRSE at 4 months postoperative compared to target MRSE
- Percent of eyes with MRSE within 0.50 D and within 1.00 D of target MRSE at 4 months postoperative
- Contrast acuity at 4 months postoperative compared to 3-month.
- Mean change in total meibomian gland score from 3 months to 4 months postoperative.
- Mean change in total SPEED score from 3 months to 4 months postoperative.
- Rates of adverse events in the Study and Control groups.
- Rates of medical and/or lens findings in the Study and Control groups.

STUDY VISITS AND PROCEDURES:

Inclusion and exclusion qualifications will be assessed at the start of Preoperative Visit #1 according to the protocol criteria. The Informed Consent Document and Authorization for Use/Disclosure of Health Information form (HIPAA authorization) must be signed by any subjects who agree to participate in the study prior to undergoing any study-specific procedures. After determination that all inclusion/exclusion criteria have been met, enrolled subjects will be randomized to either Study group or Control group in a 1:1 ratio.

Study visit schedule, procedures and key data collected at each visit are shown in **Appendix A, Appendix B, and Section 10.2, Visit Schedule, Table 1.**

DATA ANALYSIS:

Key study endpoints are the comparisons between study group and control group for precision of biometric measurements preoperatively, mean change in total Meibomian gland score at 1 month postoperatively, mean monocular UCDVA at 3 months postoperatively, rate of refractive predictability at 3 months postoperatively and rate of directed reported ocular symptoms at 3 months postoperatively. Additional endpoints will be evaluated at 1 and 3 months postoperatively for the both groups and 4 months postoperatively for crossover Control group.

Visual acuity data will be converted to LogMAR values prior to analysis. Comparisons between study group and control group for the mean monocular UCDVA at 3 months postoperatively will be performed using one-sided two-sample t-tests with alpha set at 0.05. Precision of preoperative biometric measurements is defined as the average of the three computed standard deviations from each preoperative visit. The Study group is expected to have better total Meibomian gland score at 1 month postoperatively compared to the Control group, and to have better

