20.2 KEY STUDY ENDPOINTS

- MEAN MONOCULAR UCDVA AT 3 MONTHS POSTOPERATIVE

The mean LogMAR monocular UCDVA will be reported for study group eyes and control group eyes. Note that a lower LogMAR value is a better acuity.

The success criterion is a statistically significantly lower mean LogMAR monocular UCDVA for study group eyes compared to control group eyes ($p \leq$

0.05) at 3 months postoperative. The right eyes and left eyes data from each group will also be presented.

- **PRECISION (STANDARD DEVIATION) OF PREOPERATIVE AL, ACD, AND KERATOMETRIC MEASUREMENTS (K)**

AL, ACD and K values will have three sets of measurements at the Preoperative Visit #1 and three sets of measurements at the Preoperative Visit #2. For AL, ACD and keratometry, the standard deviation of each set of measurements will be computed at both preoperative visits and the average of the three computed standard deviations from each preoperative visit is defined as the precision. The difference in precision between the two preoperative visits will be calculated for AL, ACD and K values. The precisions of the AL, ACD and keratometry measurements are expected to be better (smaller standard deviation) for study group eyes than the ones for control group eyes. The right eyes and left eyes data from each group will also be presented.

- **RATE OF REFRACTIVE PREDICTABILITY AT 3 MONTHS POSTOPERATIVE**

The frequency, proportion and 95% confidence intervals of eyes with achieved MRSE within 0.50 D and 1.00 D of targeted MRSE will be summarized at 3 months postoperatively. The proportion of study group eyes with achieved MRSE within 0.50D and within 1.00 D of targeted MRSE is expected to be greater compared to control group eyes. The right eyes and left eyes data from each group will also be presented.

- **RATE OF BOTHERSOME OCULAR SYMPTOMS AT 3 MONTHS POSTOPERATIVE**

The frequency and proportion of subjects who experienced moderate or severe ocular symptoms (halos, night glare, starburst, and night vision difficulties) will be reported. The rate of directed report bothersome ocular symptoms at 3 months postoperatively is expected to be lower for study group subjects than that for control group subjects.

- **MEAN CHANGE IN TOTAL MEIBOMIAN GLAND SCORE FROM BASELINE TO 1 MONTH POSTOPERATIVE**

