APPENDIX A DIAGRAM OF STUDY FLOW

APPENDIX B SUMMARY OF PROCEDURES REQUIRED AT EACH VISIT

Examination	Preop Visit #1	LF Tx ^d (Study Group Only)	Preop Visit #2 ^e	Operative	1-Mo. Post-op	3-Mo. Post-op and Crossover LF Tx ^f	4-Mo. Post-op (Crossover Group Only)
Informed consent, medical and ocular history, inclusion/exclusion criteria	X						
Potential visual acuity, targeted refraction, IOL power calculations, corneal topography	X		X				
IOL power/serial number, Toric power/axis (if needed)				X			
Monocular UCDVA, BCDVA	X ^c				X	X	X
Binocular UCDVA, BCDVA					X	X	X
Binocular UCIVA and UCNVA						X	X
Manifest refraction	X ^c				X	X	X
Contrast acuity testing (binocular, 10% contrast acuity and 20/40 contrast threshold)						X	X
Keratometry, biometry (repeat 3 sets of biometry / keratometry measurements)	X		X				
Meibomian gland assessment	X				X	X	X
Ocular surface staining	X		X		X		
TBUT	X		X		X		
Eyelid margin evaluation	X		X		X		
Meibomian gland imaging (LipiScan or LipiView II)	X				X		X
Biomicroscopic slit-lamp exam ^a	X	X	X		X	X	X
Fundus exam ^b	X						
Adverse events	X	X	X		X	X	X
Ocular and systemic medications	X	X	X		X	X	X
Ocular/Visual symptom assessment (non-directed)	X		X		X	X	X
SPEED and PRVSQ questionnaires	X		X			X	X

^a Includes determination of medical and lens findings/complications, lens orientation. Slit-lamp exam is performed both before and after LipiFlow treatment.

^b Fundus exam may be performed dilated with ophthalmoscopy or undilated per site practice standard of care.

^c Preoperative UCDVA, BCDVA and refraction tests will be performed per site practice standard of care.

^d Preoperative LipiFlow treatment can occur the same day or within 1 week of Preoperative Visit #1.

^e Preoperative Visit #2 will be 2-4 weeks after LipiFlow treatment for study group and be 2-4 weeks after the Preoperative Visit #1 for control group.

^f LipiFlow treatment after 3 months postop exams for the Crossover Control group only.

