PRVSQ questionnaire: Patient-Reported Visual Symptom Questionnaire (PRSVQ) will be used for the assessment. It is a directed questionnaire intended to collect information on visual symptoms. In order to minimize any effect of the doctor-patient relationship may have on a subject’s responses on the questionnaire, the study questionnaires will be self-administered by the subjects. The PRVSQ is to be administered at the start of the preoperative visits and at every follow-up visit, prior to any visual acuity testing.

SPEED Questionnaire is a self-administered, validated assessment tool designed specifically to assess frequency and severity of dry eye symptom. It is used to determine study eligibility based on none to mild dry eye symptoms at Baseline Visit and to evaluate ocular comfort at Baseline and follow-up visits. Dry eye symptoms assessed using the SPEED questionnaire are dryness, grittiness or scratchiness; soreness or irritation; burning or watering; and eye fatigue. The SPEED questionnaire is to be administered preoperatively and at designated postoperative study exams, as defined in **Appendix K**.

Tear Break-Up Time (TBUT) is measured preoperatively and at designated postoperative study exams. Three separate measurements of tear break-up time are taken for each eye using a stopwatch to record the time. For data analysis, the three measurements are averaged to represent the mean tear break-up time for each eye. The Investigator or designee measures tear break-up time under a slit-lamp biomicroscope following instillation of fluorescein dye in the eye using the Dry Eye Test (DET) method, as defined in **Appendix L**.

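### The key bothersome-symptom endpoint is reported as raw 3-month rates and leaves unused the pre-randomization PRVSQ that every subject completes, at some cost in precision and with no display of baseline balance

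*SAP*

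**What the plan says.** The Protocol synopsis (Data Analysis) lists the "rate of directed reported ocular symptoms at 3 months postoperatively" among the key Study v Control comparisons. Protocol 20.2 gives the expected direction: "The rate of directed report bothersome ocular symptoms at 3 months postoperatively is expected to be lower for study group subjects".

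SAP 4.1.4 defines what will be presented: "The frequency and proportion of subjects who experienced moderate or severe ocular symptoms (halos, night glare, starburst, and night vision difficulties) will be reported". The matching row under Key Study Endpoints in SAP Appendix I is "Rate of bothersome ocular symptoms at 3-month", given as n and % by group. Neither place has a baseline column, a covariate, a confidence interval or a test.

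Protocol Appendix D describes the PRVSQ: "It is a directed questionnaire intended to collect information on visual symptoms". On timing it says: "The PRVSQ is to be administered at the start of the preoperative visits and at every follow-up visit, prior to any visual acuity testing". In Protocol Appendix B the row "SPEED and PRVSQ questionnaires" is marked at both preoperative visits, at 3 months and at 4 months. Protocol 10.3 lists the PRVSQ among the Visit #1 examinations and requires the Visit #1 steps to be done in order, with randomization after the baseline examination.

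The Preoperative Characteristics block of SAP Appendix I has baseline rows for gland score, MGYLS, TBUT, SPEED and eyelid margin, but none for the PRVSQ.

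**The concern.** The trial collects a pre-randomization answer on the questionnaire that later supplies a key endpoint, and then sets it aside. If subjects who report moderate or severe halos or glare before surgery are also more likely to do so at 3 months, the Visit #1 answer explains part of the outcome variance, and a comparison that ignores it is less precise than it could be.

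The plan treats its other questionnaire differently. SPEED shares the PRVSQ's row in Appendix B, but has a baseline table row and is analysed as change from baseline (SAP 4.2.2). Gland score, MGYLS, staining and TBUT are also analysed as change. Randomization is stratified by site only (Protocol 10.3), so the design does not balance baseline visual symptoms.

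At stake are some power on a key endpoint for which the trial was not sized, and the reader's ability to see whether the arms started alike on it.

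**Working it through.** **1. The plan's own figure.** SAP 5 sizes the trial on UCDVA only: 55 per group, 1 line, SD 1.6 lines, one-sided 0.05. The standard error is 1.6 × √(2/55) = 0.305, and 1/0.305 − 1.645 = 1.63, which gives 94.9% power (94.7% by the noncentral t). This agrees with the SAP's claim of over 90%. Enrolment of 55/0.8 = 68.75, rounded up to 69, also reproduces. No rate, effect or power is given for the symptom endpoint.

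**2. Is Visit #1 a valid baseline?** Yes, in both arms, because the questionnaire precedes assignment. Visit #2 is not: in the Study group it falls 2–4 weeks after LipiFlow (Protocol 10.2).

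**3. Gain from adjustment.** From the documents: n = 55 per arm. Assumed: the 3-month rates, the correlation ρ between Visit #1 and 3-month status, and a one-sided 0.05 comparison borrowed from the UCDVA calculation.

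Raw SE = √[(p₁(1−p₁) + p₂(1−p₂))/55]. Adjusted SE = raw SE × √(1−ρ²). Power = Φ(difference/SE − 1.645).

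- 40% v 20%: raw SE = √[(0.24 + 0.16)/55] = 0.0853.
- 30% v 15%: raw SE = √[(0.21 + 0.1275)/55] = 0.0783.

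| ρ | variance saved | effective n per arm, 55/(1−ρ²) | power, 40% v 20% | power, 30% v 15% |
|---|---|---|---|---|
| 0 (raw) | 0% | 55 | 76% | 61% |
| 0.2 | 4% | 57.3 | 77% | 62% |
| 0.3 | 9% | 60.4 | 79% | 64% |
| 0.4 | 16% | 65.5 | 82% | 67% |

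The gain is about 1.5 points at ρ = 0.2 and about 6 points at ρ = 0.4. A second power formula gives slightly lower levels and a similar gain: for 40% v 20%, 74.5% raw, 76.1% at 0.2, 78.0% at 0.3 and 80.9% at 0.4.

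**4. Simulation check** (20,000 replicates, assumed baseline rate 40%, linear adjustment).

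- 40% v 20%, ρ = 0.4: SD of the difference 0.085 raw and 0.079 adjusted; power 76% and 82%.
- 40% v 20%, ρ = 0.2: power 76.0% raw and 76.6% adjusted.
- No effect (40% v 40%), ρ = 0.2 or 0.4: both estimates centre on zero; type I error 4.9–5.0% raw and 5.1% adjusted.

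**5. Size of a chance baseline gap.** Its SD is √(2b(1−b)/55), where b is the baseline rate: 7.6 points at b = 20% and 9.5 points at b = 50%. A gap of 10 points or more then arises in 19% to 29% of trials. Only part of it reaches the 3-month difference. In the simulation the carry-over was about 0.2 of the gap at ρ = 0.2 and 0.4 at ρ = 0.4, so a 10-point gap shifts the result by about 2 to 4 points.

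**The case against.** The strongest reply is that nothing here is an error. In a 1:1 randomized trial the raw difference in rates is unbiased, chance imbalance is already part of its standard error, and the null simulation shows type I error near 5% with or without adjustment. That stands, and it limits the point to precision and transparency.

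The correlation could also be low. Visit #1 answers are given with cataracts in place, and 3-month answers with a diffractive lens. Nothing in the documents supports 0.4, and at 0.2 the gain is negligible. That stands too, and is why the low end of the range is shown.

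Next, the power figures describe a comparison that the plan does not specify. The p ≤ 0.05 criterion is attached to UCDVA alone (SAP 4.1.1), and SAP 4.1.4 has no test or interval. The figures are therefore illustrative. Yet the endpoint is listed as a key between-group comparison, so some estimate of the difference will be read from it.

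Other key endpoints, UCDVA and refractive predictability, are also plain 3-month values. For UCDVA, power of 94.7% under the plan's inputs leaves at most 5.3 points to gain, so the point is not extended there.

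A reader might infer two stronger things. One is that chance imbalance could exceed the treatment effect. The documents state no effect. Against the assumed ones, with a 50% baseline rate (SD 9.5 points), a gap above 20 points arises in about 3.6% of trials and one above 15 points in about 12%, and only a fraction carries through. The other is that a higher correlation would bring a much larger gain. Two yes/no variables with different rates have a ceiling on their correlation. At a 50% baseline rate it is √(0.20/0.80) = 0.50 for a 20% outcome and √(0.15/0.85) = 0.42 for a 15% outcome. A lower baseline rate would raise the ceiling, but the documents support no such values.

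**Conclusion.** The point holds as a modest matter of precision and display. A pre-randomization answer to the questionnaire behind a key endpoint is collected in both arms, and is neither tabulated nor used. The raw analysis is valid. Under the assumed rates, adjustment would add between about 1.5 power points (correlation 0.2) and about 6 (correlation 0.4).

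These sizes rest on assumed 3-month rates, an assumed correlation, 55 evaluable subjects per arm and a one-sided 0.05 comparison; only the 55 is the plan's figure for this purpose. The documents do not support a claim that the endpoint is biased or that its conclusion is at risk. The case for the baseline row does not depend on the correlation: without it, a reader cannot see whether the arms were alike at entry on this outcome.

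**What to change.** - **Source.** In SAP 4.1.4, name the PRVSQ as the instrument. The SAP drops the protocol's word directed, and the non-directed assessment in Protocol 10.6 also grades halos, glare and starbursts as mild, moderate or severe, so the source should not be left to inference.
- **Estimate.** Report the Study minus Control difference in the 3-month rate standardised for Visit #1 status: a logistic model with arm and baseline moderate/severe (yes/no), expressed as a marginal risk difference with 95% CI. Keep the raw rates beside it.
- **Baseline row.** Add Visit #1 PRVSQ rates by arm to Preoperative Characteristics in SAP Appendix I.
- **Visit.** Use Visit #1 only, because Visit #2 follows LipiFlow in the Study group.

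The cost is SAP wording, one model and one table row, with no new data. There is one small downside. SAP 2.1 rules out imputation, so a subject without a Visit #1 PRVSQ leaves the adjusted model but stays in the raw rates. Report both denominators.
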